11.2. Second stage analysis – 24 months long-term follow-up (LTFU24)

11.2.1. Demographics Data and Other Baseline Characteristics

Not applicable for this stage of analysis since all information on demographics data and other baseline characteristics was already analyzed in the first stage analysis (see 11.1.1).

11.2.2. Primary Efficacy Analysis

Not applicable for this stage of analysis since all information on the primary efficacy variable was already analyzed in the first stage analysis (see 11.1.3).

11.2.3. Secondary Efficacy Analyses

Not applicable for this stage of analysis since all information on the secondary efficacy variables was already analyzed in the first stage analysis (see 11.1.4).

11.2.4. Safety Analyses

11.2.4.1. Time to Reach Complete Wound Closure

Not applicable for this stage of analysis since all information on this endpoint was already analyzed in the first stage analysis (see 11.1.5.1).

11.2.4.2. Cosmesis and Function at 12 Months from Wound Closure

Not applicable for this stage of analysis since this endpoint was already analyzed in the first stage analysis (see 11.1.5.2).

11.2.4.3. Cosmesis and Function at 24 Months from Wound Closure

The MVSS score for a patient will be calculated as described in Section 10.3.4.2. Descriptive statistics of MVSS score at 24 months will be provided by treatment group, for both observed and imputed data (for handling of missing data see Section 10.1.4.2). The treatment groups will be compared using a linear model with imputed MVSS score at 24 months as the dependent variable. The explanatory variables in the model will include treatment, and the following variables: treatment center, age, %TBSA, proportion of the FT area of a patient and

number of TWs (1,2,3-4, ≥5). The coefficient corresponding to the treatment group will be estimated and will represent the estimated mean difference in MVSS score at 24 months between NexoBrid and SoC adjusted for any imbalance in the stratification factors. The results of the regression analysis will be provided.

A clinically meaningful difference will be incorporated into the analysis that will represent a 1.9 or more units advantage to the SoC group, so that the analysis will show whether the NexoBrid group is estimated to have on average a MVSS score that is not worse by more than 1.9 units than the score for the SoC group. That is, the following hypothesis are about to be tested:

$$H_0: \Delta \ge 1.9$$
 vs. $H_1: \Delta < 1.9$

Where Δ is the mean difference in MVSS score between NexoBrid and SoC adjusted for any imbalance in the stratification factors. These hypotheses will be tested by comparing the 95% confidence interval for the coefficient of the treatment group from the linear model outlined above to the clinically meaningful difference 1.9. The null hypothesis will be rejected if the upper bound of this interval is smaller than 1.9.

The main analysis will be performed as described above using both on-site and remotely collected evaluations, with missing values imputed as described in SAP Section 10.1.4.2.

In addition, a sensitivity analysis will be performed (similar to the main analysis described above) to explore the possible influence of remotely captured data. For this sensitivity analysis, the remote evaluations will be "corrected", as described in SAP Section 10.5.2.2, and missing values at 24 months will be imputed applying the imputation procedure from SAP Section 10.1.4.2 on observed *on-site* evaluations and "corrected" *remote* evaluations.

11.2.4.4. Adverse Events

The analyses of Adverse Events described in Section 11.1.5.4 will be repeated, as deemed relevant, on the following additional sub-periods:

- adverse events occurring after the 12 months follow up (including AEs from the first stage that are still ongoing);
- o adverse events occurring during the entire study period

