7.2.3.4. Adverse Events

For each AE the following information will be determined:

- AE description
- Type of AE (General, Local TW related, Local not TW related)
- onset date and time
- outcome date and time
- outcome (resolved, resolved with sequelae, not resolved, death)
- intensity (mild, moderate, severe)
- action taken regarding study drug (yes, no)
- relation to study drug (not related, remotely related, possibly related, probably related, related)
- treatment required (none, medication, surgery, hospitalization, other)
- seriousness (serious, not serious)

Treatment-emergent Adverse Events (TEAEs) are defined as AEs that start during or after first NexoBrid or SoC treatment. TEAEs, related TEAEs, and Serious TEAEs will be summarized by Medical Dictionary for Regulatory Activities (MedDRA) system organ class, preferred term and severity. Events where the relation is considered "related", "possibly related", or "probably related" will be considered as related and events where the relation is considered 'not related' or 'remotely related' will be considered "not related". Events with missing causality will be considered as "related" and will be included in the summary of related TEAEs. Serious AEs resulting in death and AEs resulting in withdrawal from the study will be listed separately.

For randomized patients, AEs that occur between signing the informed consent document and receipt of study treatment will be provided in a listing.

Except for a summary table on event level, TEAEs will be reported on a per-patient basis. This means that even if a patient reported the same event repeatedly (i.e., events mapped to the same preferred term) during the assigned study period, the event will be counted only once in tabulations. In the latter case the event will be assigned the worst severity and the strongest relationship to the study drug. The earliest date will be regarded as start date of the event and

the latest date will be regarded as stop date of the event. All AEs, including those occurring more than once will be listed.

The same rules for counting, severity and relationship apply for PTs mapped to the same system organ class.

Notes:

- The MedDRA version will be denoted in the footnote of tables and listings.
- Listings will be sorted within patients by start date of the adverse event according to treatment group.

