EQ-5D-Y consists of 5 items with 3 possible answers each. It will be evaluated per the EQ-5D-Y user guide [20]. Note that for children aged 2 – 11 years, the parent/caregiver will complete a proxy version of the EQ-5D for the patient, children aged 12-18 will complete the

questionnaire themselves. EQ-5D will not be assessed for children younger than 2 years (based on age of first FU visit).

For each item, relative and absolute frequencies of the answers will be computed in total and per age group, defined in the stratification variables (see Section 11.1.11). The table will be presented by treatment arm and overall. The analysis will be done per age at randomization. Furthermore, summary statistics of the EQ VAS will be computed in total and per age group. The table will be presented by treatment arm and overall.

The EQ-5D states will be converted to a single summary index using the USA value set from [21]. For subjects with incomplete questionnaires, the summary index will be a missing value.

Immunogenicity Evaluation

The immunogenicity evaluation will be done in a separate analysis and is described in a separate document.

Pyrexia and Hypothermia

Pyrexia (and related terms) and hypothermia reported as AEs will be presented in the AEs tables.

Systemic Infection

Systemic infections reported as AEs will be presented in the AEs tables.

Adverse Events

Counts and frequencies of subjects reporting treatment emergent adverse events (TEAEs), related TEAEs, and serious TEAEs per treatment arm will be computed per system organ class (SOC) and preferred term (PT). This will be done separately by:

- Severity (mild / moderate / severe AEs)
- Relatedness (not related or remotely related / possibly related or probably related or related AEs)

Time of onset (during the treatment session / within 24 hours after treatment / 24 – 72 hours after treatment / more than 72 hours up to the end of the first week after treatment / during week 2 to week 4 after treatment / more than 4 weeks after treatment)

Note: During the treatment session is defined as the time frame from start date/time of first eschar removal procedure to end date/time of last eschar removal procedure.

All serious adverse events will be listed for the enrolled population.

For more details see Section 11.1.5.4.

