For each of the two stages of analysis (see Section 11 for details), the safety data gathered in that stage will be analyzed separately. That is, in the first stage analysis (acute + 12M follow-up), all AEs reported until the 12 months follow-up will be analyzed separately for the following sub-periods: 1) until the 12 weeks follow-up, 2) between the 12 weeks follow-up and the 12 months follow-up (including AEs from the first sub-period that are still ongoing), 3) combined until the 12 months follow-up. In the second stage analysis (24 months follow-up), all AEs reported between the 12 months follow-up and the 24 months follow-up (including AEs from the first stage that are still ongoing) will be analyzed. Furthermore, a combined analysis, including all reported AEs, will be provided at the end of the trial.

Central Laboratory Values

For all analyses involving data from the central laboratory only samples taken within the allowed time range are considered

- Pre procedure: Within 12 hours before start of the procedure until up to 15 min after start.
- Post procedure: Within 24 hours after end of the procedure

Samples not taken in the allowed time range are excluded from the analysis.

Imputation of data from the central laboratory is only done for planned missing values. Version 10.01 of the study protocol specifies some planned missing laboratory samples. On the one hand, a laboratory sample before the additional application of NexoBrid is not required. On the other hand, a laboratory sample before a nonsurgical procedure is only prescribed for the first eschar removal procedure and a laboratory sample after a nonsurgical procedure is only

required for the last eschar removal procedure. To enable analysis of pre-post differences on procedure level, the planned missing values are imputed as follows:

- Planned missing measurements before an additional application / a non-surgical procedure
 - Values of a sample taken after the previous eschar removal procedure are used if the laboratory sample was taken within 12 hours before start of the eschar removal procedure.
- Planned missing measurements after a non-surgical procedure
 Values of a sample taken before the subsequent eschar removal procedure are used if the laboratory sample was taken within 24 hours after end of the nonsurgical procedure.

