11.1.5.4. Adverse Events

In this analysis, only the treatment emergent adverse events occurring until the 12 months follow-up visit will be analyzed.

All adverse events will be listed. Furthermore, the following tables will be produced separately for the following sub-periods: 1) until the 12 weeks follow-up, 2) between the 12 weeks follow-up and the 12 months follow-up (including AEs from the first sub-period that are still ongoing), 3) combined until the 12 months follow-up:

- Summary of Treatment Emergent Adverse Events (TEAEs) on a subject level and on an event level
- Summary of TEAEs by System Organ Class (SOC), and Preferred Term (PT) separately for:
 - All TEAEs

- Treatment related TEAEs
- o General and local, not TW-related TEAEs
- Local, TW-related TEAEs
- Summary of Special Interest TEAEs by PT (for sub-period 1), separately for:
 - TEAEs with PTs associated with fever (Pyrexia, Body Temperature Increased, Hyperthermia)
 - TEAEs associated with target wound infections (only if Local, TW-related: relevant preferred terms will be reviewed after finalization of coding and can include for example preferred terms as: Wound Infection Bacterial, Staphylococcal Skin Infection, Wound Infection, Wound Infection Staphylococcal if reported as local TW-related)
 - TEAEs associated with target wound pain (relevant preferred terms will be reviewed after finalization of coding)
- Summary of TEAEs by SOC, PT, and time of onset (for sub-period 1) separately for:
 - o All TEAEs
 - General and local, not TW-related TEAEs
 - Local, TW-related TEAEs
 - All Treatment Emergent Serious Adverse Events (TESAEs)
- Summary of TEAE by SOC, PT and maximum intensity. In this table, patients who
 experienced multiple AEs with the same PT, but different intensities will be counted
 only once per PT with their maximum intensity. Subjects with multiple AEs with the
 same SOC but different intensities will be counted only once per SOC with their
 maximum intensity in the SOC row. This table will be produced separately for:
 - All TEAEs
 - Treatment related TEAEs
 - General and local, not TW-related Treatment related TEAEs
 - o Local, TW-related Treatment related TEAEs
 - All TESAEs
 - Treatment related TESAEs

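### The later-period AE tables count earlier events still ongoing together with events that start in the period, so new late-onset AEs by arm cannot be read directly from them

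*SAP*

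**What the plan says.** The SAP divides AE reporting into periods.

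- **First stage.** SAP 11.1.5.4 lists three sub-periods: up to 12 weeks, 12 weeks to 12 months, and combined up to 12 months. The second carries earlier events forward, "including AEs from the first sub-period that are still ongoing". SAP 10.3.4.4 states the same rule: "between the 12 weeks follow-up and the 12 months follow-up (including AEs from the first sub-period that are still ongoing".
- **Second stage.** SAP 11.2.4.4 repeats the first-stage tables, so far as considered relevant, for two further periods. One is "adverse events occurring after the 12 months follow up (including AEs from the first stage that are still ongoing" and the other is the entire study. SAP 10.3.4.4 agrees: "all AEs reported between the 12 months follow-up and the 24 months follow-up (including AEs from the first stage that are still ongoing".
- **Time of onset.** SAP 11.1.5.4 plans a "Summary of TEAEs by SOC, PT, and time of onset (for sub-period 1) separately for" several event groups. The last onset category in SAP 10.3.4.4 is open-ended: "more than 4 weeks after treatment".
- **Counting.** Under SAP 7.2.3.4, when a patient has the same preferred term more than once within a period, "the event will be counted only once in tabulations", with the worst severity and strongest relationship. One summary table is on event level.
- **Listings.** Onset date and time are collected for each AE (SAP 7.2.3.4), and all AEs are listed.

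**The concern.** A reader will look to the tables for the later periods to see whether one arm develops more new problems long after treatment. As defined, a patient enters a later-period row in either of two ways: by having an AE that starts in the period, or by having an earlier one that has not resolved. The row does not show which. In the second stage the carried-over group is any first-stage AE still ongoing, with onset at any time up to 12 months, so it is not confined to the acute phase.

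Two other rules bear on this. SAP 10.1.1 imputes a missing AE end date to the end of the analysis stage or study termination, so an event with no recorded stop date can count as ongoing. The maximum-intensity tables use the recorded intensity. If one intensity is held per event, an event that was severe only early on appears as severe in the later period. The SAP does not say how changes in severity are recorded, so this second effect is conditional.

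At stake is how well the long-term AE comparison can be read: persistence of old events and appearance of new ones are different safety messages.

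**Working it through.** The plan gives no figure on this point, so there is nothing to reproduce. The check has three steps.

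**1. Does any planned table isolate new late onset?** The later-period tables (SAP 11.1.5.4 sub-period 2; 11.2.4.4) include carried-over events. The onset tables cover sub-period 1 only. Even if they were repeated for a later period, an event starting in week 6 and one starting in month 15 would share the last, open-ended category. So no planned table isolates it.

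**2. Can it be derived from the cumulative tables?** Patients with an event over the entire study, minus patients with an event up to 12 months, equals patients whose first event in that row came after 12 months. The same holds for 12 months minus 12 weeks. This recovers first-ever onset per row, but not:
- a recurrence of the same preferred term, because the patient is already counted;
- a different new event in a SOC or any-TEAE row where the patient already had an event. For example, a patient with one term in week 2 and another term of the same SOC in month 15 contributes zero to the subtracted SOC row, although the new preferred-term row does show the event.

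Subtraction also needs matching tables in both stages, and the second-stage set is produced only so far as considered relevant.

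**3. How could the mixture look?** All rates here are assumed; the documents give none. Let new-onset rates be a (NexoBrid) and b (SoC), and carry-over rates cN and cS, independent of new onset within a row. The tabulated rates are 1 − (1 − a)(1 − cN) and 1 − (1 − b)(1 − cS).

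With a = 10% and b = 3%:

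| Carry-over NexoBrid / SoC | Tabulated NexoBrid | Tabulated SoC | Ratio | Difference (points) |
|---|---|---|---|---|
| 0 / 0 | 10.0% | 3.0% | 3.33 | 7.0 |
| 5% / 5% | 14.5% | 7.85% | 1.85 | 6.65 |
| 10% / 10% | 19.0% | 12.7% | 1.50 | 6.3 |
| 20% / 20% | 28.0% | 22.4% | 1.25 | 5.6 |
| 30% / 30% | 37.0% | 32.1% | 1.15 | 4.9 |
| 5% / 15% | 14.5% | 17.55% | 0.83 | −3.05 |
| 15% / 5% | 23.5% | 7.85% | 2.99 | 15.65 |

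With equal carry-over c, the difference is (a − b)(1 − c), so it shrinks slowly while the ratio falls quickly. At 10% carry-over, the share of patients in the row with only an old event is (19.0 − 10.0)/19.0 = 47% for NexoBrid and (12.7 − 3.0)/12.7 = 76% for SoC.

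With a = 15% and b = 5%, the ratio goes from 3.00 to 1.97, 1.62, 1.33 and 1.21 at equal carry-over of 5, 10, 20 and 30%. Carry-over of 5% versus 15% gives 19.25% in both arms, which hides the difference completely.

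If no patient has both kinds of event, equal carry-over leaves the difference unchanged. Taking about 72 per arm (145/2), 10 versus 2 new events plus 15 carried over in each arm gives 25 versus 17. The ratio falls from 5.0 to 1.47, and the difference is 8/72 = 11.1 points both ways.

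**The case against.** The case for leaving the plan alone has substance.

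- **Nothing is lost or hidden.** The rule is stated openly wherever it applies, and it matches the rule for concomitant medications (SAP 11.1.5.12 and 11.2.4.5). Onset dates are recorded, all AEs are listed, and cumulative tables are planned. This stands: it is a matter of presentation. The listing, however, leaves the reader to rebuild the by-arm comparison, and subtraction is only partial.
- **Tables of AEs present in a period are legitimate.** Persisting sequelae matter after burns. This also stands; the difficulty is only that the two kinds of event are not shown apart.
- **Most tables run by SOC and preferred term.** A new late harm appears in its own preferred-term row, mixed only with carried-over events of the same term. This stands and limits the effect in those rows. It helps less in the SOC and any-TEAE rows.
- **Late harm is also assessed elsewhere.** MVSS, LEFS, QuickDASH, range of motion and EQ-5D at 24 months are unaffected.

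Three stronger readings are tempting, and the documents do not support them. A reader might infer that a late excess is always diluted. With unequal carry-over the distortion can go either way, and with equal carry-over it falls mainly on the ratio. A reader might infer that a significant late signal would lose significance, but the SAP plans no test of AE counts, and SAP 11.2.8 calls all second-stage testing exploratory. A reader might also take "The earliest date will be regarded as start date of the event" to turn a late recurrence into an old event. That merge works within the assigned study period and matters only where onset date is tabulated, which is sub-period 1. In a later-period table the patient counts once either way.

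**Conclusion.** The point holds as a limitation of presentation. Both later-period sets of AE tables combine earlier events still ongoing with events that start in the period, and no planned table separates them. New late-onset AEs by arm therefore cannot be read directly from these tables, and subtraction of cumulative tables gives only first-ever onset per row.

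The size cannot be computed from the documents. The figures above rest on assumed new-onset and carry-over rates, and most also assume independence between the two. They show direction and sensitivity only: similar carry-over in both arms lowers the relative difference, and unequal carry-over can mask, reverse or exaggerate it. They are not an estimate of what happened in this trial.

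It would be wrong to infer that late harm cannot be found or that data are biased or lost. The change is a cheap improvement to descriptive tables, not the correction of an error.

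**What to change.** In SAP 11.1.5.4 (sub-period 2) and 11.2.4.4, with matching wording in 10.3.4.4:

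1. Tabulate TEAEs with onset in the period as one set of counts, including recurrences that start in it.
2. Show AEs with earlier onset that are still ongoing at the start of the period in a separate column.
3. Run the later-period intensity and relatedness tables on the onset-in-period events.
4. State how an AE whose start or end date was imputed under SAP 10.1.1 is classified in this split.

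The cost is a few lines of SAP wording, one onset flag derived from dates already collected, and slightly longer tables. No new data collection is needed.

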11.2.4.5. Concomitant Medications

In this analysis, only the concomitant medications given after the 12 months follow up (including CM with a start date before the 12 months follow up but an end date after that or still ongoing) will be analyzed.

The number of concomitant medication and patients involved will be tabulated with overall numbers and with reference to ATC coding using the Level 2 and Level 4 codes.

11.2.4.6. Lower Extremity Function Scale (LEFS)

The LEFS scores at 24 months follow up assessment will be presented by treatment group using descriptive statistics. The mean LEFS scores between treatment groups will be compared by a one-way analysis of variance.

11.2.4.7. Disabilities of the Arm, Shoulder and Hand (QuickDASH)

The QuickDASH scores at 24 months follow up assessment will be presented by treatment group using descriptive statistics. The mean QuickDASH scores between treatment groups will be compared by a one-way analysis of variance.

11.2.4.8. Range of Motion (ROM)

The ROM will be evaluated using a variable with 2 levels (all measurements normal / at least one abnormal finding). Summary tables will be provided giving sample size, absolute and relative frequency and 95% CI (Confidence Interval) for the proportion with a normal score, separately for each study treatment group.

A logistic regression model will be applied for testing the statistical significance of the difference in ROM measurements between NexoBrid and SoC treatments at 24 months. Adjustment will be made for any imbalance between the groups in treatment center, overall treated %TBSA and % of FT per patient.

Only subjects with joint injury will be regarded for this analysis. A footnote to the results will indicate this.

